Expiratory muscle function in critically ill ventilated patients

NTC:

Date of approved by METC: February 14, 2017

Date of amendment approved by METC: May 22, 2019

Rationale	
Inspiratory muscle weakness develops rapidly in ventilated critically ill patients¹⁻⁴ and is associated with adverse outcome, including prolonged duration of mechanical ventilation and mortality.⁵⁻⁷ Surprisingly, the effects of critical illness on expiratory muscle function have not been studied.
 
The main expiratory muscles are the abdominal wall muscles, including the external oblique (EO), internal oblique (IO) and transversus abdominis muscles (TRA).^{8,9} These muscles are activated when respiratory drive or load increases, which can be during e.g. exercise,¹⁰⁻¹² diaphragm fatigue,¹³ increased airway resistance, or positive airway pressure ventilation.¹⁴ The abdominal wall muscles are also critical for protective reflexes, such as coughing.¹⁵ Reduced abdominal muscles strength may lead to decreased cough function^{16,17} and thus inadequate airway clearance.¹⁸ This will lead to secretion pooling in the lower airways, atelectasis, and ventilator associated pneumonia (VAP).^{19,20} Studies have shown that decreased cough function is a risk for weaning failure and (re)hospitalization for respiratory complications.²¹ Further, high mortality was found in patients with low peak expiratory flow.²²
 
Considering the importance of a proper expiratory muscle function in critically ill patients, it is surprising that the prevalence, causes, and functional impact of changes in expiratory abdominal muscles thickness during mechanical ventilation (MV) for critically ill patients are still unknown.

------------------	--

Ultrasound is increasingly used in the ICU for the visualization of respiratory muscles. In a recent pilot study we confirmed the feasibility and reliability of using of ultrasound to evaluate both diaphragm and expiratory abdominal muscle thickness in ventilated critically ill patients (manuscript in preparation). An example of such measurement can be found in figure 1. Accordingly, the primary aim of the present study is to evaluate the evolution of abdominal expiratory muscle thickness during MV in adult critically ill patients, using ultrasound data.

Figure 1. Left: ultrasound of the abdominal expiratory muscles (EO, IO, TRA). Right: anatomical overview of the abdominal muscles. RA = rectus abdominis, less involved in respiration

Objective

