Primary objective: to establish the effects of critical illness and mechanical ventilation on thickness of the abdominal expiratory muscles.

Secondary objectives:

- to establish the effect of changes in abdominal expiratory muscle thickness on the expiratory muscle function.

	
 - to establish the correlation between changes in thickness of the abdominal expiratory and inspiratory muscles. - to study whether changes in the thickness of the abdominal expiratory muscles also affects weaning outcome, and ICU readmission due to respiratory complications.
Study design	Prospective cohort study.
Study population	Patients who have been mechanically ventilated at the intensive care unit (ICU)
Inclusive criteria	
 - Age > 18 years - Invasive mechanical ventilation < 48 hours - Expected duration of mechanical ventilation > 72 hours
Exclusive criteria	
 - Past medical history of neuromuscular disorders - Mechanical ventilation > 48 hours within the current hospital admission - BMI > 35 kg/m² - Pregnant women - Open abdominal wounds at proposed location of the ultrasound probe, due to recent abdominal surgery
Sample size	100 subjects
Recruiting subjects	
Because mechanical ventilation is a requirement for eligibility, the participants frequently will be incapable of consent at the time of inclusion. Therefore, we will ask delayed informed consent from the patient as soon as he/she is capable of providing consent.
 
If patients are not able to give consent during their hospital stay, we will send an opt-out letter to the patient.

Intervention	Data from ultrasound measurements and from the electronic patient record will be obtained / analyzed. One additional blood sample will be obtained within 24 hours after inclusion, during planned blood collection (from arterial line or venous puncture).
Study endpoint	- Thickness of the abdominal expiratory muscles (external oblique, internal oblique, transverse abdominis muscle), during the inspiratory and expiratory phases of breathing.

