Study parameters	
 - Thickness of the diaphragm muscle - Inflammatory markers (TNF-alpha, IL-6, IL-10) at inclusion (measured from blood sample using ELISA technique). - Respiratory function parameters: maximum inspiratory pressure (MIP), maximum expiratory pressure (MEP), cough peak flow (CPF), diaphragm pressure and diaphragm electrical activity (in selected patients with these measurements available in clinical practice). - Mechanical ventilation parameters. - Weaning outcome - Ventilator associated pneumonia (VAP) - Follow-up of 6 weeks: readmission to ICU / hospital, reason for readmission, pneumonia acquired after discharge when subject is hospitalized. - Critical illness parameters (e.g. medication, APACHE II score) - Patient characteristics (e.g. gender, age, neurological and cardiopulmonary co-morbidities, BMI) 
This data will be retrieved from the electronic patient record and anonymously filed in a database.
 
Data on muscle thickness (thickness of diaphragm muscle and expiratory muscles) will be collected directly

	from ultrasound measurements on the ultrasound device.

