	
expiratory muscle thickness and change in diaphragm thickness will be assessed with a Student's t-test that is paired per subject. This will be done by using the change in thickness between baseline and the last data point obtained. Second, this will be evaluated by using the slope of the thickness curves assessed with a goodness of fit model. We will use a goodness of fit model to first describe the course of both diaphragm and expiratory muscle thickness for each subject. The type of model will be determined after data is obtained.
 
Subgroup analysis
 
Based on the outcomes of these analyses, a subgroup analysis may be performed to compare the subjects with high change in expiratory muscle thickness, to a group with low change in expiratory muscle thickness. A cutoff value to divide these groups will be determined based on how data will emerge. Variables as respiratory function measurements can be compared between groups with a Student's t-test, using group average values. Further, a Kaplan-Meier survival analysis will be carried out to quantify differences in time to wean between groups.

Referenties
	

- and endotracheal tube pressure with bilateral anterolateral magnetic phrenic nerve stimulation in patients in the intensive care unit. *Crit Care Med* 2001; 29:1325-31.

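### Kaplan-Meier is named for time to wean with no handling of death on the ventilator, so the curves may overstate the proportion weaned and misstate the group difference in either direction

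*Combined protocol and SAP*

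**What the plan says.** Under Subgroup analysis in the Statistical Analysis Plan, "a subgroup analysis may be performed to compare the subjects with high change in expiratory muscle thickness" with those whose thickness changes little. The dividing line is left open: "A cutoff value to divide these groups will be determined based on how data will emerge". For these two groups, "a Kaplan-Meier survival analysis will be carried out to quantify differences in time to wean between groups". The result bears on the secondary objective about weaning outcome.

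The plan gives no weaning event definition, time origin, horizon, censoring rule or test for this analysis, and names no competing-risk method. Weaning outcome appears under Study parameters without a definition. Death is not listed there, and the follow-up item covers other events: "Follow-up of 6 weeks: readmission to ICU / hospital, reason for readmission, pneumonia acquired after discharge when subject is hospitalized".

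Two other places bear on how likely deaths are. The inclusion criteria require "Expected duration of mechanical ventilation > 72 hours". The Rationale says that inspiratory muscle weakness "is associated with adverse outcome, including prolonged duration of mechanical ventilation and mortality", and that "high mortality was found in patients with low peak expiratory flow".

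**The concern.** Weaning is the event of interest, and death on the ventilator rules it out. Censoring a patient at death treats that patient as still able to be weaned later, at the rate seen in those who remain. The complement of the Kaplan-Meier curve then describes weaning in a setting where nobody dies, not the share of patients who came off the ventilator.

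Two things follow. The level is too high in any group with deaths before weaning. And if the groups differ in mortality, the gap between the curves is not the gap in proportion weaned. The Rationale makes a mortality difference plausible without establishing it. At stake is the only time-to-event analysis that the plan names for the weaning objective.

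**Working it through.** **Inputs.** From the documents: 100 subjects and the Kaplan-Meier method. The plan has no figure on this point to reproduce, since it gives no weaning rate, death rate, group split or horizon. Assumed here: constant daily hazards of weaning (w) and of death on the ventilator (d), 50 patients per group, a 28-day horizon and a two-sided 5% test.

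**Formulas.** With deaths censored, the displayed proportion weaned is 1 − exp(−w·t). The proportion actually weaned is w/(w+d) × [1 − exp(−(w+d)·t)]. The two agree only when d = 0.

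**Case A: equal weaning, unequal death** (w = 0.10 in both groups; d = 0.02 and 0.05).
- Displayed, both groups: 1 − exp(−2.8) = 93.9%.
- Actual, d = 0.02: 0.10/0.12 × [1 − exp(−3.36)] = 80.4%.
- Actual, d = 0.05: 0.10/0.15 × [1 − exp(−4.2)] = 65.7%.

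The curves show no gap, while the proportions weaned differ by about 15 points.

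**Case B: the opposite error** (w = 0.10 and 0.06; d = 0.04 and 0.02).
- Displayed: 93.9% and 1 − exp(−1.68) = 81.4%, about 13 points apart.
- Actual: 0.10/0.14 × [1 − exp(−3.92)] = 70.0% and 0.06/0.08 × [1 − exp(−2.24)] = 67.0%, about 3 points apart.

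Here the curves exaggerate the gap.

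**Range of overstatement.** For w from 0.05 to 0.12/day, d/(w+d) from 10% to 40%, and a horizon of 28 or 42 days, the displayed proportion exceeds the actual one by 4 to 39 points.

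**Effect on a test.** Simulated trials of 50 versus 50 to day 28 compared a log-rank test with deaths censored against the same test with the dead kept at risk as never weaned. With no other censoring, the second follows the cumulative incidence, as Gray's test does.

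| Weaning/day | Death/day | Deaths censored | Dead kept as never weaned |
|---|---|---|---|
| 0.10 vs 0.10 | 0.02 vs 0.05 | about 5% | about 24% |
| 0.10 vs 0.10 | 0.02 vs 0.03 | about 5% | about 9% (8% in a longer run) |
| 0.10 vs 0.08 | 0.02 vs 0.05 | about 15% | about 54% |
| 0.10 vs 0.06 | 0.03 vs 0.03 | about 55% | about 40% |
| 0.10 vs 0.06 | 0.04 vs 0.02 | about 56% | about 14% |

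In the first two rows the weaning hazards are equal, so 5% is the correct error rate for a test of those hazards. It is not lost power.

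**The case against.** The strongest reply is that the plan does not say deaths will be censored. A reader might infer that naming Kaplan-Meier implies this, and that the estimator is therefore wrong. The text does not go that far. If the dead were kept at risk to a fixed day, with no other censoring, 1 minus Kaplan-Meier would equal the cumulative incidence. This part of the objection stands: the overstatement is conditional on the usual practice. But the plan does not state the alternative rule either.

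Second, a log-rank test with deaths censored is a valid comparison of weaning hazards under independent censoring, and that is a defensible reading of an objective about an effect on weaning. This also stands. It does not rescue the curves as a statement of how many patients were weaned, and the plan uses them to quantify differences.

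Third, a reader might take the Rationale as proof that deaths will be unequal between the groups. It is not. One statement concerns inspiratory weakness and the other concerns low peak expiratory flow. Judging by titles in the reference list, the sources cited there include one on one-year mortality after ventilation and one on extubation outcomes. The Rationale itself says the functional impact of expiratory thickness change is not known. Unequal deaths are plausible, no more.

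Finally, the analysis is optional and rests on a cutoff chosen from the data, so its reach is small.

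**Conclusion.** The concern holds in a limited form. The plan names Kaplan-Meier for an event that death precludes, without handling death. Under the usual censoring, the proportion weaned is overstated by 4 to 39 points over the assumed range, and by nothing if nobody dies before weaning. The group difference can be hidden (Case A) or inflated (Case B).

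It would be tempting to conclude that Kaplan-Meier necessarily masks a difference, or that a competing-risk test is always more sensitive. The last two rows of the table show otherwise. The two approaches answer different questions, and both answers are needed.

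All rates, the equal split and the horizon are assumptions. The documents give no mortality figure, so the actual size for this cohort is unknown. The point is worth correcting, but it touches only an optional subgroup analysis for a secondary objective. The primary endpoint, change in muscle thickness, is unaffected.

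**What to change.** Replace the Kaplan-Meier sentence under Subgroup analysis with:

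> Time to wean will be described by the cumulative incidence of weaning (Aalen-Johansen) with death on the ventilator as a competing event, compared by Gray's test; cause-specific hazards of weaning and of death will be reported alongside.

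Add date of death to the data taken from the electronic patient record. The same passage should define the weaning event, time origin and horizon, and say how transfer while still ventilated is censored.

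The main change costs one sentence and one field from a record already being searched, and R, which the plan already names, has standard routines. There are two downsides. The weaning and death estimates must be read together, and Gray's test can be less sensitive than the cause-specific comparison to a difference in weaning rate alone, which is why both are reported. The change does not resolve the data-driven cutoff or the definition of groups by thickness change measured after inclusion; those are separate matters.
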